2.8.1 Adverse events (AEs)

All treatment emergent adverse events starting on or after the first dose of study treatment and until the last dose of study treatment plus 7 days (30 days for serious adverse events [SAEs]) will be included in all summaries and listings.

The definition for "treatment emergent" is as below:

- events started after the first dose of study medication or events present prior to the first dose of study medication but increased in severity based on preferred term
- and started prior to the last dose plus 7 days (inclusive)

All adverse events will be coded using MedDRA dictionary and summarized by Primary system organ class (SOC) and preferred term (PT)using frequency and percentage.

Primary system organ classes will be sorted alphabetically and within each primary system organ class, the preferred terms will be sorted in descending order of frequency.

If a patient reported more than one adverse event with the same preferred term, the adverse event will be counted only once. If a patient reported more than one adverse event within the same primary system organ class, the patient will be counted only once at the system organ class level.

Adverse events will be summarized by presenting, for each treatment group, the number and percentage of patients having any adverse event, having an adverse event in each body system and having each individual adverse event.

Summaries will also be presented for AEs by severity and for study treatment related AEs. If a particular AE 'severity' is missing, this variable will be listed as missing and treated as missing in summaries. If a patient reported more than one adverse event with the same preferred term, the adverse event with the greatest severity will be presented. If a patient reported more than one adverse event within the same primary system organ class, the patient will be counted only once with the greatest severity at the system organ class level, where applicable.

Any other information collected (e.g., severity or relatedness to study medication) will be listed, as appropriate.

The most common adverse events reported ($\geq z$ % in any group for each preferred term in the table by SOC and PT) will be presented in descending frequency according to its incidence in secukinumab group starting from the most common event. Here threshold value z is set to 2 (%) but it may be updated following review of the dry run outputs.

Serious Adverse Event (SAE)

Number and percentage of patients with serious adverse events, regardless of study drug relationship, will be presented by primary system organ class and preferred term. Primary system organ classes will be sorted alphabetically and, within each primary system organ class, the preferred terms will be sorted in descending order of frequency.

All SAEs will be listed.

If a patient reported more than one adverse event with the same preferred term, the adverse event will be counted only once. If a patient reported more than one adverse event within the same primary system organ class, the patient will be counted only once at the system organ class level.

Separate summaries will be provided for deaths, serious adverse events, other significant adverse events leading to discontinuation and adverse events leading to dose adjustment or interruption.

Algorithms for date imputations will be provided in Section 5.1.2.

Adverse events and serious adverse events up to and including Week 12 visit will be included in the database for the analysis at the primary analysis time point (Week 12). All Adverse events and serious adverse events will be included in the final database analysis (Week 53).

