2.3.1 Patient disposition

The number of patients screened will be presented along with the reasons for screen failures for all patients as specified in the screening phase disposition eCRF.

The number and percentage of patients in the randomized set (RAN) who, completed study periods (double-blind treatment period and open-label treatment period) and who discontinued the study prematurely including the reason for discontinuation will be presented for each treatment group and all patients.

Patients withdrawing consent will be listed with reason for withdrawal.

The number and percentage of patients with protocol deviations will be tabulated by treatment groups and listed separately by treatment groups.

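### SAP 2.8.1 gives conflicting end points for adverse-event reporting; its 7-day limit is inconsistent with protocol Section 9 and, if programmed literally, drops completers' non-serious events on Days 345 to 372

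*SAP*

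**What the plan says.** SAP 2.8.1 addresses the reporting period several times:

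- **Opening sentence.** Treatment-emergent events from first dose to the "last dose of study treatment plus 7 days (30 days for serious adverse events [SAEs]) will be included in all summaries and listings".
- **Treatment-emergent definition.** The event must begin after first dose, or be present before it and worsen, "and started prior to the last dose plus 7 days (inclusive". This bound has no longer limit for SAEs.
- **Coding sentence.** "All adverse events will be coded using MedDRA dictionary and summarized", with no end date.
- **SAE part.** "All SAEs will be listed", again with no end date, and "Separate summaries will be provided for deaths, serious adverse events, other significant adverse events leading to discontinuation".
- **Closing sentences.** For the first lock, "Adverse events and serious adverse events up to and including Week 12 visit will be included in the database for the analysis"; for the second, "All Adverse events and serious adverse events will be included in the final database analysis (Week 53". Protocol 9.5.2 has the same pair of statements.

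Three other places bear on which rule governs. The opening of protocol Section 9 has safety data summarised for every week through Week 53. SAP 2.1 says the analysis follows protocol Section 9. SAP section 4, where departures from the protocol's analyses would be declared, declares none.

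On collection, protocol 7.1 gathers AEs from consent to the end-of-study visit. The protocol summary schedules punch biopsies at Baseline, Week 12 and Week 52. Protocol 3.1.5 brings patients back about seven days after the Week 52 biopsy (visit F1) to remove sutures and check safety.

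**The concern.** Two programmers working from SAP 2.8.1 could build different AE tables, each with a sentence to point to. One would stop at last dose + 7 days and the other would run to Week 53.

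The difference matters because a completer's last dose is at Week 48, while the last biopsy is at Week 52 and its safety check at Week 53. Under the short window, the report would omit events that the protocol collects on purpose. Protocol 3.6 names infection and bleeding as risks, alongside the scar expected after each biopsy.

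There is a second effect. With four-weekly dosing, an AE that makes a patient stop can begin more than seven days after what turns out to be the last dose. The disposition table would still give the cause, because SAP 2.3.1 says that patients "who discontinued the study prematurely including the reason for discontinuation will be presented for each treatment group and all patients". The AE tables might not show it.

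**Working it through.** **Inputs.** The last dose for completers is at Week 48 (protocol 3.1.4). Nominal days come from protocol Table 6-1: Week 4 = Day 29, Week 8 = Day 57, Week 12 = Day 85, Week 48 = Day 337, Week 52 = Day 365, Week 53/F1 = Day 372. The window lengths are those of SAP 2.8.1.

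**1. Reproduce the nominal days.** Day = 7 × week + 1. Week 48: 336 + 1 = 337. Week 52: 364 + 1 = 365. Week 53: 371 + 1 = 372. All match the table.

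**2. Completer, non-serious AE, 7-day limit taken literally.**
- Last day inside: 337 + 7 = 344.
- Days outside with F1: 345 to 372, which is 372 − 344 = 28 days, and 28/372 = 7.5% of nominal study days.
- Days outside without F1: 345 to 365, which is 365 − 344 = 21 days.
- The Week 52 biopsy is 365 − 344 = 21 days past the limit, so every non-serious AE that it causes is outside.

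The limiting sentence covers listings as well as summaries, and 2.8.1 plans no other listing of non-serious AEs that would catch these.

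**3. Completer, SAE.**
- Opening sentence: 337 + 30 = Day 367.
- Definition bullet: 337 + 7 = Day 344.
- Days 345 to 367 (23 days) are inside one rule and outside the other.
- Days 368 to 372 (5 days) are outside both, although the same section promises a listing of all SAEs.

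**4. Comparison with the SAP's exposure rule.** SAP 2.4.1 ends exposure at the earlier of the last visit and last dose + 84 days: min(372, 337 + 84 = 421) = Day 372. The last 28 days therefore count as exposure while their non-serious AEs would not be counted.

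**5. Non-serious AE that leads to stopping before the next four-weekly dose.** Onset 0 to 7 days after the dose is inside. Onset 8 to 27 days after is outside, which is 20 of the 28 interval days. Before Week 12 this affects two intervals:
- dose Day 29, limit Day 36, Days 37 to 56 outside;
- dose Day 57, limit Day 64, Days 65 to 84 outside.

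Weekly doses leave no gap, because + 7 days reaches the next dose. These are calendar days, not proportions of events. The documents give no rate from which to estimate how many patients would be affected.

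**6. Which rule has more support.**

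| Reading | Support |
|---|---|
| Stop at last dose + 7 days (SAEs + 30) | SAP 2.8.1 opening sentence; its bullet for 7 days only |
| Include everything to Week 53 | SAP 2.8.1 closing sentence; protocol 9.5.2; protocol Section 9 opening; SAP 2.1; SAP section 4 |

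**The case against.** The strongest reply is that the documents already settle the matter. The SAP follows protocol Section 9 and declares no change from it, and that section has safety data summarised through Week 53. That statement is about summaries, so it also answers the suggestion that the closing sentences of 2.8.1 describe only what the database holds at each lock. The opening sentence of 2.8.1 also never says that only those events are included, so it could be read as a minimum. This carries weight: full inclusion is the better-supported reading. It does not remove the defect, because 2.8.1 still contains an explicit 7-day definition and an SAE limit that disagrees with it, and a programmer may simply implement them.

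Some stronger conclusions are tempting, and the documents do not support them:

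- **That biopsy events will be lost.** They are lost only if the 7-day limit is applied literally.
- **That SAEs after the last visit are dropped from the tables.** Protocol 7.2.2 governs reporting to the sponsor's safety department for 30 days after that visit. The documents do not say whether those SAEs enter the clinical database, and Section 9 ends at Week 53.
- **That each omitted patient moves a rate by a fixed 1/50 or 1/25.** SAP 2.8.1 counts a patient once per preferred term and once per organ class, so a row changes only if the patient has no other qualifying event in it.
- **That AEs leading to discontinuation must go missing.** The sentence planning that summary does not restate the limit, so they may.

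It is also fair to say that an on-treatment window is a legitimate display. The objection here is to conflicting windows, and to a limit that reaches the listings.

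**Conclusion.** The point stands as an internal contradiction in SAP 2.8.1, and as a limit inconsistent with the protocol section that the SAP says it follows.

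If full inclusion governs, or the opening sentence is only a minimum, nothing is lost. If the limit is programmed literally, a completer's non-serious AEs starting in the last 28 nominal days (21 without F1) appear nowhere, including every non-serious AE from the Week 52 biopsy. SAE summaries differ by 23 days between the two 2.8.1 limits. Some AEs that made patients stop may be absent from their own summary, in unknown number.

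The day counts assume the nominal schedule; actual dates shift them slightly. Events that began by Day 344 and continued are still included. An event with a partial start date may be imputed into the window under SAP 5.1.2.

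The consequence is bounded. Efficacy is unaffected. For completers the loss falls in the open-label phase only; it reaches the placebo-controlled period only through patients who stop before Week 12. Baseline and Week 12 biopsy events of patients who continue dosing are not cut off.

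**What to change.** In SAP 2.8.1, replace the end bound in the opening sentence and the second bullet with one rule that matches protocol Section 9. Keep the first bullet, so that pre-dose events that worsen still count. Suggested text:

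*In the final analysis, AEs and SAEs that start or worsen after first dose are summarised through the end-of-study visit (F1/Week 53 if held); this includes the summary of AEs leading to discontinuation. All AEs and SAEs in the database are listed, and those with onset later than last dose + 7 days (SAEs: + 30 days) are flagged.*

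If an on-treatment table is kept as an additional display, state one SAE limit and use it in both places. The Week 12 analysis keeps its own cut-off.

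The cost is a wording change, one derivation rule and one listing flag; SAP 2.8.4.2 already plans an on-treatment flag for vital signs. The downside is slightly higher AE counts, including some events remote from dosing, which the flag identifies.

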2.8.1.1 Adverse events of special interest / grouping of AEs

Not applicable.

2.8.2 Deaths

Separate summaries and listings will be provided for deaths for each treatment period.

2.8.3 Laboratory data

The following laboratory variables will be analyzed:

- Hematology, which includes:
 - hemoglobin, hematocrit, red blood cell count, white blood cell count with differential (neutrophils including bands, lymphocytes, monocytes, eosinophils, basophils) and platelet count
- Clinical chemistry, which includes:

urea, creatinine, total bilirubin, alanine transaminase (ALT)/serum glutamic pyruvate transaminase (SGPT), aspartate transaminase (AST)/serum glutamic oxaloacetic transaminase (SGOT), gamma glutamyl transpeptidatse (GGT), and alkaline phosphatase

- High-sensitivity C-reactive protine (hs CRP)
- Hemoglobin A1c
- Fasting laboratory evaluations
 - Plasma glucose
 - Insulin
 - Lipids
- Viral serology
 - Hepatitis screening: Hepatitis B surface antigen (HBsAg); Hepatitis C virus antibody (HCVAb)
 - HIV screening: HIV 1/2

Descriptive summary statistics for the change from baseline to study visit will be presented by laboratory variable and weight stratum and treatment group. Change from baseline will only be summarized for patients with both baseline and post-baseline values and will be calculated as: change from baseline = post-baseline value - baseline value.

The following laboratory variables will be analyzed with respect to the notable ranges:

Table 2-6 Criteria for notable abnormalities of hematology values

Variables	Notable abnormalities
Hemoglobin	≥ 2.0 g/dL decrease from baseline
Platelet count	< Lower Limit of Normal (LLN) White
blood cell	< 0.8 x LLN
Neutrophils	< 0.9 x LLN
Eosinophils	> 1.1 x ULN
Lymphocytes	> 1.1 x ULN

Table 2-7 Criteria for notable abnormalities of clinical chemistry values

Variables	Notable abnormalities	
Liver function and related variables:		
ALT (SGPT)	> 3 x Upper Limit of Normal (ULN)	
AST (SGOT)	> 3 x ULN	
Total bilirubin	> 1.5 x ULN	
Alkaline phosphatase	> 2 x ULN	
Renal function and electrolyte variables		
Creatinine (serum)	> 1.5 x ULN	

For each variable, the maximum change (maximum decrease and maximum increase) from baseline, within treatment period, will be summarized analogously.

In addition, shift tables will be provided for all variables to compare a patient's baseline laboratory evaluation relative to the visit's observed value. For the shift tables, the reference laboratory ranges will be used to evaluate whether a particular laboratory test value was normal, low, or high for each visit value relative to whether or not the baseline value was normal, low, or high. If appropriate, the shifts to the most extreme laboratory test value within a treatment phase (either initial or entire) will be presented as well (including category "high and low"). These summaries will be presented by laboratory variable and treatment group.

2.8.4 Other safety data

2.8.4.1 ECG and cardiac imaging data

Not applicable.

2.8.4.2 Vital signs

Descriptive summary statistics for change from baseline for each post-baseline visit will be presented by vital signs, weight stratum, and treatment groups, as appropriate. Change from baseline will be calculated only for the patients with both baseline and post-baseline values and will be calculated as: change from baseline = post-baseline value - baseline value

The number and the percentage of patients with notable vital signs will be presented. The criteria for notable vital sign abnormalities are provided in Table 2-3 below:

Table 2-8 Criteria for notable vital sign abnormalities

Vital signs (unit)	Normal measure	Notable abnormality
Systolic blood pressure (mmHg)	90 to <120 mmHg	>= 140 mmHg (hypertension) or < 90 mmHg (hypotension)
Diastolic blood pressure (mmHg)	60 to <80 mmHg	>= 90 mmHg (hypertension) or < 60 mmHg (hypotension)
Pulse (bpm)	60 to 100(bpm)	> 100 bpm (tachycardia) or < 60 bpm (bradycardia)

Note: Blood pressure indicative

- Hypertension if systolic blood pressure of ≥140 mmHg and/or diastolic blood pressure of ≥90 mmHg
- Hypotension if systolic blood pressure of <90 mmHg and/or a diastolic blood pressure of <60 mmHg
- A blood pressure indicative of prehypertension (systolic blood pressure of 120 to <140 mmHg and/or diastolic blood pressure of 80 to <90 mmHg) will not be regarded as notable (Chobanian, Bakris, and Black 2003).

A listing of the newly-occurring notably abnormal vital sign will be provided.

All vital signs will be listed with "on-treatment" flag displayed.

2.9 Pharmacokinetic endpoints

Not applicable.

2.10 PD and PK/PD analyses

Not applicable.

2.11 Patient-reported outcomes

Not applicable.

SAP 0

Novartis For business use only Page 28

2.14 Interim analysis

The database of this study will be locked twice, first after the end of double-blind treatment period (Week 12) and again at the end of the follow-up period (Week 53). Data analyses will follow each database lock. The main analysis for the primary objective will be done at Week 12. As Week 12 analysis considered primary and no specific hypothesis is preidentified for testing, adjustment of significance level due to this interim analysis is irrelevant.

3 Sample size calculation

The table below considers total sample sizes of 75 patients (50 in secukinumab group and 25 in placebo group) and 99 patients (66 in secukinumab group and 33 in placebo group) to estimate the difference between the two groups with respect to the pooled estimate of the two percentages of patients who have the "event" at Week 12 for each of the two primary efficacy variables. The table shows "margin of error" (half-width of confidence interval) for a twosided 95% confidence interval (Julious and Patterson, 2004; Kianifard and Islam, 2011; nQuery Advisor 7.0).

0

Based on the results in the above table, it was decided that approximately 75 randomized patients (50 in secukinumab group and 25 in placebo group) will be randomized in this exploratory study to estimate the difference in response rates between the two treatment groups.

4 Change to protocol specified analyses

Not applicable.

5 Appendix

5.1 Imputation rules

5.1.1 Study drug

Any partial dates will be imputed as follows:

We take the earlier day of

- The last day in the month and
- The calculated end day of the corresponding epoch

5.1.2 AE date imputation

Impute AE end date:

- 1. If the AE end date 'month' is missing, the imputed end date should be set to the earliest of the (min (last visit date, last dose date + 84 days), 31DECYYYY, date of death).
- 2. If the AE end date 'day' is missing, the imputed end date should be set to the earliest of the (min (last visit date, last dose date + 84 days), last day of the month, date of death).
- 3. If AE 'year' is missing or AE is ongoing, the end date will not be imputed.

Impute AE start date:

Before imputing AE start date, find the AE start reference date.

1. If the (imputed) AE end date is complete and the (imputed) AE end date < treatment start date then AE start reference date = min (informed consent date, earliest visit date).

- 2. Else AE start reference date = treatment start date
- 1. If the AE start date 'year' value is missing, the date uncertainty is too high to impute a rational date. Therefore, if the AE year value is missing, the imputed AE start date is set to NULL.
- 2. If the AE start date 'year' value is less than the treatment start date year value, the AE started before treatment. Therefore:
 - a. If AE 'month' is missing, the imputed AE start date is set to the mid-year point (01JulYYYY).
 - b. Else if AE 'month' is not missing, the imputed AE start date is set to the mid-month point (15MONYYYY).
- 3. If the AE start date year value is greater than the treatment start date year value, the AE started after treatment. Therefore:
 - a. If the AE month is missing, the imputed AE start date is set to the year start point (01JanYYYY).
 - b. Else if the AE month is not missing, the imputed AE start date is set to the later of (month start point (01MONYYYY), AE start reference date + 1 day).
- 4. If the AE start date year value is equal to the treatment start date year value:
 - a. And the AE month is missing the imputed AE start date is set to the AE reference start date + 1 day.
 - b. Else if the AE month is less than the treatment start month, the imputed AE start date is set to the mid-month point (15MONYYYY).
 - c. Else if the AE month is equal to the treatment start date month or greater than the treatment start date month, the imputed AE start date is set to the later of (month start point (01MONYYYY), AE start reference date + 1 day).

If complete (imputed) AE end date is available and the imputed AE start date is greater than the (imputed) AE end date, then imputed AE start date should be set to the (imputed) AE end date.

Page 32

5.1.3 Concomitant medication date imputation

Impute CM end date:

- 1. If CM end day is missing and CM month/year are non-missing then impute CM day as the minimum of treatment end date and the last day of the month.
- 2. If CM end day/month are missing and CM year is non-missing then impute CM day as the minimum of treatment end date and the end of the year (31DECYYYY).
- 3. If imputed CM end date is less than the CM start date, use the CM start date as the imputed CM end date.

Impute CM start date:

- 1. If the CM start date year value is missing, the imputed CM start date is set to one day prior to treatment start date.
- 2. If the CM start date year value is less than the treatment start date year value, the CM started before treatment. Therefore:
 - a. If the CM month is missing, the imputed CM start date is set to the mid-year point (01JulYYYY).
 - b. Else if the CM month is not missing, the imputed CM start date is set to the midmonth point (15MONYYYY).
- 3. If the CM start date year value is greater than the treatment start date year value, the CM started after treatment. Therefore:
 - a. If the CM month is missing, the imputed CM start date is set to the year start point (01JanYYYY).
 - b. Else if the CM month is not missing, the imputed CM start date is set to the month start point (01MONYYYY).
- 4. If the CM starts date year value is equal to the treatment start date year value:
 - a. And the CM month is missing or the CM month is equal to the treatment start date month, then the imputed CM start date is set to one day prior treatment start date.
 - b. Else if the CM month is less than the treatment start date month, the imputed CM start date is set to the mid-month point (15MONYYYY).

SAP 0

c. Else if the CM month is greater than the treatment start date month, the imputed CM start date is set to the month start point (01MONYYYY).

If complete (imputed) CM end date is available and the imputed CM start date is greater than the (imputed) CM end date, then imputed CM start date should be set to the (imputed) CM end date.

